### **5.3.5.6 Abnormal Vital Sign Values**

Not every vital sign abnormality qualifies as an adverse event. A vital sign result must be reported as an adverse event if it meets any of the following criteria:

- Is accompanied by clinical symptoms
- Results in a change in study treatment (e.g., dosage modification, treatment interruption, or treatment discontinuation)
- Results in a medical intervention or a change in concomitant therapy
- Is clinically significant in the investigator's judgment

It is the investigator's responsibility to review all vital sign findings. Medical and scientific judgment should be exercised in deciding whether an isolated vital sign abnormality should be classified as an adverse event.

If a clinically significant vital sign abnormality is a sign of a disease or syndrome (e.g., high blood pressure), only the diagnosis (i.e., hypertension) should be recorded on the Adverse Event eCRF.

Observations of the same clinically significant vital sign abnormality from visit to visit should only be recorded once on the Adverse Event eCRF (see Section 5.3.5.4 for details on recording persistent adverse events).

### 5.3.5.7 Abnormal Liver Function Tests

The finding of an elevated ALT or AST ( $> 3 \times \text{ULN}$ ) in combination with either an elevated total bilirubin ( $> 2 \times \text{ULN}$ ) or clinical jaundice in the absence of cholestasis or other causes of hyperbilirubinemia is considered to be an indicator of severe liver injury (as defined by Hy's law). Therefore, investigators must report as an adverse event the occurrence of either of the following:

- Treatment-emergent ALT or AST  $> 3 \times \text{ULN}$  in combination with total bilirubin  $> 2 \times \text{ULN}$
- Treatment-emergent ALT or AST  $> 3 \times \text{ULN}$  in combination with clinical jaundice

The most appropriate diagnosis or (if a diagnosis cannot be established) the abnormal laboratory values should be recorded on the Adverse Event eCRF (see Section 5.3.5.2) and reported to the Sponsor immediately (i.e., no more than 24 hours after learning of the event), either as a serious adverse event or an adverse event of special interest (see Section 5.4.2).

### 5.3.5.8 Deaths

All deaths that occur during the protocol-specified adverse event reporting period (see Section 5.3.1), regardless of relationship to study drug, must be recorded on the Adverse Event eCRF and immediately reported to the Sponsor (see Section 5.4.2). This includes death attributed to progression of AD.

Death should be considered an outcome and not a distinct event. The event or condition that caused or contributed to the fatal outcome should be recorded as the single medical concept on the Adverse Event eCRF. Generally, only one such event should be reported. The term "**sudden death**" should be used only for the occurrence of an abrupt and unexpected death due to presumed cardiac causes in a patient with or without preexisting heart disease, within 1 hour after the onset of acute symptoms or, in the case of an unwitnessed death, within 24 hours after the patient was last seen alive and stable. If the cause of death is unknown and cannot be ascertained at the time of reporting, "**unexplained death**" should be recorded on the Adverse Event eCRF. If the cause of death later becomes available (e.g., after autopsy), "unexplained death" should be replaced by the established cause of death.

If the death is attributed to progression of Alzheimer's disease, "Alzheimer's disease progression" should be recorded on the Adverse Event eCRF.

Deaths that occur after the adverse event reporting period should be reported as described in Section 5.6.

### 5.3.5.9 Preexisting Medical Conditions

A preexisting medical condition is one that is present at the screening visit for this study. Such conditions should be recorded on the General Medical History and Baseline Conditions eCRF.

A preexisting medical condition should be recorded as an adverse event only if the frequency, severity, or character of the condition worsens during the study. When recording such events on the Adverse Event eCRF, it is important to convey the concept that the preexisting condition has changed by including applicable descriptors (e.g., "more frequent headaches").

#### **5.3.5.10 Lack of Efficacy or Worsening of Alzheimer's Disease**

Events that are clearly consistent with the expected pattern of progression of the underlying disease should not be recorded as adverse events. These data will be captured as efficacy assessment data only. In most cases, the expected pattern of progression will be based on guidelines (e.g., NIAAA New Diagnostic Criteria and Guidelines for AD; see [Appendix 2](#) and [Appendix 3](#)). In rare cases, the determination of clinical progression will be based on symptomatic deterioration. However, every effort should be made to document progression through use of objective criteria. If there is any uncertainty as to whether an event is due to disease progression, it should be reported as an adverse event.

#### **5.3.5.11 Hospitalization or Prolonged Hospitalization**

Any adverse event that results in hospitalization (i.e., inpatient admission to a hospital) or prolonged hospitalization should be documented and reported as a serious adverse event (per the definition of serious adverse event in Section [5.2.2](#)), except as outlined below.

The following hospitalization scenarios are not considered to be adverse events:

- Hospitalization for respite care
- Planned hospitalization required by the protocol (e.g., for study drug administration or insertion of access device for study drug administration)
- Hospitalization for a preexisting condition, provided that all of the following criteria are met:

The hospitalization was planned prior to the study or was scheduled during the study when elective surgery became necessary because of the expected normal progression of the disease

The patient has not experienced an adverse event.

#### **5.3.5.12 Adverse Events Associated with an Overdose or Error in Drug Administration**

An overdose is the accidental or intentional use of a drug in an amount higher than the dose being studied. An overdose or incorrect administration of study treatment is not itself an adverse event, but it may result in an adverse event. All adverse events associated with an overdose or incorrect administration of study drug should be recorded on the Adverse Event eCRF. If the associated adverse event fulfills seriousness criteria, the event should be reported to the Sponsor immediately (i.e., no more than 24 hours after learning of the event; see Section [5.4.2](#)).

### 5.3.5.13 Patient-Reported Outcome Data

Adverse event reports will not be derived from *PRO* data by the Sponsor, and safety analyses will not be performed using *PRO* data. *Investigators and site staff* are not expected to review *PRO* data for adverse events.

## 5.4 IMMEDIATE REPORTING REQUIREMENTS FROM INVESTIGATOR TO SPONSOR

Certain events require immediate reporting to allow the Sponsor to take appropriate measures to address potential new risks in a clinical trial. The investigator must report such events to the Sponsor immediately; under no circumstances should reporting take place more than 24 hours after the investigator learns of the event. The following is a list of events that the investigator must report to the Sponsor within 24 hours after learning of the event, regardless of relationship to study drug:

- Serious adverse events (see Section 5.4.2 for further details)
- Adverse events of special interest (see Section 5.4.2 for further details)
- Pregnancies (see Section 5.4.3 for further details)

The investigator must report new significant follow-up information for these events to the Sponsor immediately (i.e., no more than 24 hours after becoming aware of the information). New significant information includes the following:

- New signs or symptoms or a change in the diagnosis
- Significant new diagnostic test results
- Change in causality based on new information
- Change in the event's outcome, including recovery
- Additional narrative information on the clinical course of the event

Investigators must also comply with local requirements for reporting serious adverse events to the local health authority and IRB/EC.

## **5.4.2 Reporting Requirements for Serious Adverse Events, Adverse Events of Special Interest, and PET Ligand Adverse Events**

### **5.4.2.1 Events That Occur prior to Study Drug Initiation**

After informed consent has been obtained but prior to initiation of study drug, serious adverse events caused by a protocol-mandated intervention *as well as all serious adverse events that occur within 48 hours of PET ligand administration regardless of causality* should be reported. The Serious Adverse Event/Adverse Event of Special Interest Reporting *paper* Form provided to investigators should be completed and submitted to the Sponsor or its designee immediately (i.e., no more than 24 hours after learning of the event), either by faxing or by scanning and emailing the form using the fax number or email address provided to investigators.

*For PET ligand-related adverse events, the clinical site will complete a PET ligand-specific non-serious adverse event reporting paper form and submit it to the Sponsor or its designee by scanning and emailing the form using the email address provided on the form.*

### **5.4.2.2 Events That Occur after Study Drug Initiation**

After initiation of study drug, serious adverse events and adverse events of special interest will be reported until 8 weeks after the last dose of study drug. Investigators should record all case details that can be gathered immediately (i.e., within 24 hours after learning of the event) on the Adverse Event eCRF and submit the report via the electronic data capture (EDC) system. A report will be generated and sent to Roche Safety Risk Management by the EDC system.

In the event that the EDC system is unavailable, the Serious Adverse Event/Adverse Event of Special Interest Reporting Form provided to investigators should be completed and submitted to the Sponsor or its designee immediately (i.e., no more than 24 hours after learning of the event), either by faxing or by scanning and emailing the form using the fax number or email address provided to investigators. Once the EDC system is available, all information will need to be entered and submitted via the EDC system.

Instructions for reporting serious adverse events that occur >8 weeks after the last dose of study treatment are provided in Section 5.6.

## **5.4.3 Reporting Requirements for Pregnancies**

### **5.4.3.1 Pregnancies in Female Patients**

Female patients of childbearing potential will be instructed to immediately inform the investigator if they become pregnant during the study or within 8 weeks after the last dose of study drug. A Clinical Trial Pregnancy Reporting Form should be completed and

submitted to the Sponsor or its designee immediately (i.e., no more than 24 hours after learning of the pregnancy), either by faxing or by scanning and emailing the form using the fax number or email address provided to investigators. Pregnancy should not be recorded on the Adverse Event eCRF. The investigator should discontinue study drug and counsel the patient, discussing the risks of the pregnancy and the possible effects on the fetus. Monitoring of the patient should continue until conclusion of the pregnancy. Any serious adverse events associated with the pregnancy (e.g., an event in the fetus, an event in the mother during or after the pregnancy, or a congenital anomaly/birth defect in the child) should be reported on the Adverse Event eCRF. In addition, the investigator will submit a Clinical Trial Pregnancy Reporting Form when updated information on the course and outcome of the pregnancy becomes available.

#### **5.4.3.2 Pregnancies in Female Partners of Male Patients**

Male patients will be instructed through the Informed Consent Form to immediately inform the investigator if their partner becomes pregnant during the study or within 8 weeks after the last dose of study drug. A Clinical Trial Pregnancy Reporting Form should be completed and submitted to the Sponsor or its designee immediately (i.e., no more than 24 hours after learning of the pregnancy), either by faxing or by scanning and emailing the form using the fax number or email address provided to investigators. Attempts should be made to collect and report details of the course and outcome of any pregnancy in the partner of a male patient exposed to study drug. The pregnant partner will need to sign an Authorization for Use and Disclosure of Pregnancy Health Information to allow for follow-up on her pregnancy. After the authorization has been signed, the investigator will submit a Clinical Trial Pregnancy Reporting Form when updated information on the course and outcome of the pregnancy becomes available. An investigator who is contacted by the male patient or his pregnant partner may provide information on the risks of the pregnancy and the possible effects on the fetus, to support an informed decision in cooperation with the treating physician and/or obstetrician.

#### **5.4.3.3 Abortions**

Any abortion should be classified as a serious adverse event (as the Sponsor considers abortions to be medically significant), recorded on the Adverse Event eCRF, and reported to the Sponsor immediately (i.e., no more than 24 hours after learning of the event; see Section [5.4.2](#)).

#### **5.4.3.4 Congenital Anomalies/Birth Defects**

Any congenital anomaly/birth defect in a child born to a female patient exposed to study drug or the female partner of a male patient exposed to study drug should be classified as a serious adverse event, recorded on the Adverse Event eCRF, and reported to the Sponsor immediately (i.e., no more than 24 hours after learning of the event; see Section [5.4.2](#)).

## **5.5 FOLLOW-UP OF PATIENTS AFTER ADVERSE EVENTS**

### **5.5.1 Investigator Follow-Up**

The investigator should follow each adverse event until the event has resolved to baseline grade or better, the event is assessed as stable by the investigator, the patient is lost to follow-up, or the patient withdraws consent. Every effort should be made to follow all serious adverse events considered to be related to study drug or trial-related procedures until a final outcome can be reported.

During the study period, resolution of adverse events (with dates) should be documented on the Adverse Event eCRF and in the patient's medical record to facilitate source data verification.

All pregnancies reported during the study should be followed until pregnancy outcome.

### **5.5.2 Sponsor Follow-Up**

For serious adverse events, adverse events of special interest, and pregnancies, the Sponsor or a designee may follow up by telephone, fax, electronic mail, and/or a monitoring visit to obtain additional case details and outcome information (e.g., from hospital discharge summaries, consultant reports, autopsy reports) in order to perform an independent medical assessment of the reported case.

## **5.6 ADVERSE EVENTS THAT OCCUR AFTER THE ADVERSE EVENT REPORTING PERIOD**

The Sponsor should be notified if the investigator becomes aware of any serious adverse event that occurs after the end of the adverse event reporting period (defined as 8 weeks after the last dose of study drug), if the event is believed to be related to prior study drug treatment. These events should be reported through use of the Adverse Event eCRF. However, if the EDC system is not available, the investigator should report these events directly to the Sponsor or its designee, either by faxing or by scanning and emailing the Serious Adverse Event/Adverse Event of Special Interest Reporting Form using the fax number or email address provided to investigators.

## **5.7 EXPEDITED REPORTING TO HEALTH AUTHORITIES, INVESTIGATORS, INSTITUTIONAL REVIEW BOARDS, AND ETHICS COMMITTEES**

The Sponsor will promptly evaluate all serious adverse events and adverse events of special interest against cumulative product experience to identify and expeditiously communicate possible new safety findings to investigators, IRBs, ECs, and applicable health authorities based on applicable legislation.

To determine reporting requirements for single adverse event cases, the Sponsor will assess the expectedness of these events using the following reference document:

- Crenezumab Investigator's Brochure

To determine reporting requirements for PET ligands used, in those countries that have health authority approval of the PET ligands the approved local product information will be used. In countries where the PET ligand does not have health authority approval, the Investigator's Brochure will be used.

The Sponsor will compare the severity of each event and the cumulative event frequency reported for the study with the severity and frequency reported in the applicable reference document.

Reporting requirements will also be based on the investigator's assessment of causality and seriousness, with allowance for upgrading by the Sponsor as needed.

## **6. STATISTICAL CONSIDERATIONS AND ANALYSIS PLAN**

The purpose of this study is to investigate the treatment effect of crenezumab relative to placebo. The primary efficacy analysis will be based on an intent-to-treat (ITT) population, which will include all randomized patients who receive at least one dose of study drug, with patients grouped according to their randomly assigned treatment.

Approximately 750 patients will be randomized in the Global Enrollment Phase of this study. [REDACTED]

[REDACTED]. The China subpopulation will include patients enrolled at sites in *mainland China, Hong Kong, and/or Taiwan (according to applicable Chinese regulations)* during both the Global Enrollment Phase and the China Extension Phase.

The primary analyses of this study will include patients enrolled during the Global Enrollment Phase; data from patients enrolled *after the close of Global Enrollment* will be included in analyses separate from the primary analyses.

### **6.1 *DETERMINATION OF SAMPLE SIZE***

Determination of sample size is based on patients enrolled in the Global Enrollment Phase. In this study, 750 patients will be enrolled with 375 patients per treatment arm (crenezumab or placebo) during the Global Enrollment Phase. [REDACTED]

The estimate of sample size required to demonstrate efficacy with regard to CDR-SB is based on the following assumptions:

- The mean change in CDR-SB from baseline to Week 105 is 2.6 points in the placebo arm

- A common SD across treatment arms for change from baseline to Week 105 in CDR-SB of approximately 3.07 (this corresponds to a coefficient of variation of 118% for change in CDR-SB from baseline to Week 105 in a prodromal to mild AD population in the placebo arm)
- The dose level has a true effect of a 30% relative reduction in deterioration of CDR-SB
- 35% of randomized patients will dropout by Week 105

This sample size will have 80% power to detect a true treatment effect of 30% relative reduction in deterioration of CDR-SB at 2-sided  $\alpha$  of 0.05.

In the event that the rescue strategy or change in dose is required, the number of patients enrolled in the new dose group and its concurrently enrolled placebo arm will be 750 patients (375 patients per treatment arm) during the Global Enrollment Phase. All patients already enrolled on 60 mg/kg of *study treatment* and corresponding concurrently enrolled placebo patients will be replaced with new patients.

*A blinded assessment of the pooled standard deviation of CDR-SB change from baseline will be performed by the Sponsor at a specified timepoint prior to unblinding. As a result, the sample size may be increased from 750 up to 1126 patients (563 patients per arm). Further details will be described in the Statistical Analysis Plan (SAP). The sample size will not be reduced on the basis of this assessment. Other factors external to the study may also trigger a decision to increase sample size.*

## **6.2 SUMMARIES OF CONDUCT OF STUDY**

Enrollment, patient disposition, and incidence of protocol deviations will be summarized for *all randomized patients and grouped according to randomized treatment assignment*.

## **6.3 SUMMARIES OF TREATMENT GROUP COMPARABILITY**

Demographic and baseline characteristics (such as age, sex, race, disease severity, *APOE $\epsilon$ 4* status, use and non-use of background therapy for AD) will be summarized descriptively for the ITT population, grouped according to the assigned treatment arm.

Descriptive summaries of continuous data will present the mean, SD, median, minimum, and maximum. Descriptive summaries of discrete data will include frequencies expressed in terms of number and percentage of patients.

The primary and secondary efficacy analyses will include all randomized patients, with patients grouped according to the treatment assigned at randomization.

## **6.4 EFFICACY ANALYSES**

### **6.4.1 Primary Efficacy Endpoint**

The primary efficacy outcome measure is the change in CDR-SB from baseline (Week 1) to Week 105. For this primary outcome measure, the difference in mean change from

baseline to Week 105 between crenezumab- and placebo-treated patients will be estimated. Mixed model repeated measures (MMRMs) adjusting for disease severity, *APOE $\epsilon$ 4* status, geographic region, and the use or non-use of anti-dementia medications at baseline will be used to estimate the mean change from baseline for the primary endpoint. The analysis will include all randomized patients, with patients grouped according to the treatment assigned at randomization.

The MMRM model will be used to estimate the mean change from baseline for the primary endpoint. The model will include the change from baseline in CDR-SB as the dependent variable. The effects in the model will include baseline score, treatment group, visit, treatment-by-visit interaction and baseline score-by-visit interaction. Visit week will be treated as the repeated variable within a patient. Patient, treatment, and visit week will be treated as class variables. An unstructured variance-covariance structure will be applied to model the within-patient errors; in case of non-convergence, compound symmetry will be used.

The difference in the changes from baseline of each dose group from placebo will be estimated at each time point. The 95% CI and p-value for treatment difference will be presented.

All efforts will be made to minimize missing data. The Sponsor plans to request patients who discontinued early from study treatment to return for collection of safety and limited efficacy data until Week 105. To explore the robustness of MMRM results for the primary efficacy conclusions, sensitivity analyses (for example, using multiple imputation and pattern mixture models) will be performed. Descriptive summaries of the number of patients with missing data and the timing and reasons for discontinuation from study by treatment group will also be provided.

Additional details will be documented in the *SAP*.

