### **Statistical Methods**

#### **Primary Analysis**

The primary efficacy outcome measure is the change in CDR-SB from baseline (Week 1) to Week 105. For this primary outcome measure, the difference in mean change from baseline to Week 105 between crenezumab- and placebo-treated patients will be estimated *using* mixed model repeated measures (MMRMs) adjusting for disease severity, *APOEε4* status, geographic region, and the use or non-use of anti-dementia medications at baseline will be used to estimate the mean change from baseline for the primary endpoint. The analysis will include randomized patients *during the Global Enrollment Phase*, with patients grouped according to the treatment assigned at randomization. *Data from patients enrolled after the close of Global Enrollment will be included in analyses separate from the primary analyses.*

The MMRM model will be used to estimate the mean change from baseline for the primary endpoint. The model will include the change from baseline in CDR-SB as the dependent variable. The effects in the model will include baseline score, treatment group, visit, treatment-by-visit interaction and baseline score-by-visit interaction. Visit week will be treated as the repeated variable within a patient. Patient, treatment, and visit week will be treated as class variables. An unstructured variance-covariance structure will be applied to model the within-patient errors; in case of non-convergence, compound symmetry will be used.

The difference in the changes from baseline of each dose group from placebo will be estimated at each time point. The 95% CI and p-value for treatment difference will be presented.

All efforts will be made to minimize missing data. The Sponsor plans to request patients who discontinued early from study treatment *to* return for collection of safety and limited efficacy data until Week 105. To explore the robustness of MMRM results for the primary efficacy conclusions, sensitivity analyses (for example, using multiple imputation and pattern mixture models) will be performed. Descriptive summaries of the number of patients with missing data

and the timing and reasons for discontinuation from study by treatment group will also be provided.

Additional details will be documented in the Statistical Analysis Plan (SAP).

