Biomarker assessments (including positron emission tomography [PET] imaging of amyloid and cerebrospinal fluid [CSF] assessments) have confirmed that pAD represents a relatively early stage in the continuum of AD. Mild AD (mAD) represents a stage of the disease where patients have *not only* cognitive, *but also* clear functional deficits. *The specificity of the clinical diagnosis of mild AD can also be increased by confirming biomarker changes associated with AD (McKhann et al. 2011).* *Classification schemes of AD are an area of ongoing research and are expected to evolve further (e.g., A/T/N; see Jack et al. 2016).*

For potential patients for this clinical trial, evaluations include a thorough clinical assessment as well as measurement of disease relevant biomarkers, i.e., markers of amyloid accumulation in CSF or on brain PET scans. Patients to be enrolled may be at the clinical stage of MCI (pAD) or mild dementia and will have positive biomarkers indicative of AD. (Albert et al. 2011; McKhann et al. 2011).

The rate of AD progression shows great inter-individual variability with survival dependent on many factors, including age at onset. Population studies (Brookmeyer et al. 2002; Larson et al. 2004) suggest a lag of approximately 5 years between symptom onset and diagnosis (Roberson et al. 2005; Waring et al. 2005). Thereafter, the median survival time following a diagnosis of AD depends strongly on the patient's age at diagnosis. The median survival time ranges from 8.3 years for persons diagnosed with AD at age 65 years to 3.4 years for persons diagnosed at age 90 years (Brookmeyer et al. 2002). On average, individuals live for 3–9 years after diagnosis of AD (Helzner et al. 2008), and some survive as long as 20 years.

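### The primary MMRM could adjust for baseline ADAS-Cog-13 and age, already scheduled for every patient: a cheap possible gain in precision, not an error in the plan

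*Combined protocol and SAP*

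**What the plan says.** Section 6.4.1 and the synopsis (Primary Analysis) describe the same model. One sentence names four adjustment factors: disease severity, APOE ε4 status, "geographic region, and the use or non-use of anti-dementia medications at baseline will be used to estimate the mean change from baseline". These correspond to the stratification factors in Section 4.3. A later sentence lists the model terms: "The effects in the model will include baseline score, treatment group, visit, treatment-by-visit interaction and baseline score-by-visit interaction". That list does not repeat the four factors, so the full model has to be pieced together from two places. Further detail is deferred to the SAP, and no separate SAP text stands in the combined document.

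More baseline information is scheduled than the model uses. Section 4.6.8.1 and Appendix 1 place CDR and ADAS-Cog-13 at screening. Section 4.6.8.2 and Appendix 1 place both again at Week 1, before dosing. Section 4.6.2 records age at screening. Of these, only Week 1 CDR-SB enters the primary model as stated.

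Section 6.1 sizes the trial on "A common SD across treatment arms for change from baseline to Week 105 in CDR-SB of approximately 3.07". It presents this as the SD of the change itself and claims no reduction from covariates.

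**The concern.** The SD of the primary endpoint exceeds its assumed placebo mean, and the trial is powered at about 80% with little margin. Under randomization, a baseline covariate fixed in advance leaves the treatment estimate unbiased. If it predicts the Week 105 change beyond the terms already in the model, it also narrows the confidence interval. ADAS-Cog-13 and age need no new visits or data. Leaving them out may forgo some precision that the trial could have for a change of wording. What is at stake is a modest amount of power; neither bias nor type I error is affected.

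**Working it through.** **Inputs (Section 6.1).**
- Placebo change: "The mean change in CDR-SB from baseline to Week 105 is 2.6 points in the placebo arm".
- SD of change: 3.07.
- Effect: "The dose level has a true effect of a 30% relative reduction in deterioration of CDR-SB".
- Dropout: "35% of randomized patients will dropout by Week 105".
- 375 patients per arm, two-sided α of 0.05.

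**The plan's own figure.**
- Difference: 0.30 × 2.6 = 0.78 points. CV: 3.07 / 2.6 = 118%, as stated.
- Evaluable patients needed per arm: 2 × (1.960 + 0.842)² × 3.07² / 0.78² = 243.2, so 244. Then 244 / 0.65 = 376 per arm, against the stated 375.
- Evaluable patients planned per arm: 375 × 0.65 = 243.75. Standard error: 3.07 × √(2 / 243.75) = 0.278. Ratio: 0.78 / 0.278 = 2.805. Power: Φ(2.805 − 1.960) = 80.1%. The stated 80% is reproduced.

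**Gain from added covariates.** Let R² be the share of residual variance that the new covariates explain beyond the planned terms. The SD becomes 3.07 × √(1 − R²). The R² values are assumptions. The table applies them to the SD of 3.07, as if the planned covariates explained nothing, and leaves out the parameter cost.

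| Assumed extra R² | SD | Power at N = 750 |
|---|---|---|
| 0 | 3.07 | 80.1% |
| 2% | 3.04 | 80.9% |
| 5% | 2.99 | 82.1% |
| 10% | 2.91 | 84.1% |

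**Allowing for the planned covariates.** Suppose baseline CDR-SB and the four factors already explain 10% of the variance. The SD is then 3.07 × √0.90 = 2.91, and power starts at 84.1%. A further 5% gives 3.07 × √(0.90 × 0.95) = 2.84 and 85.8%, a gain of 1.8 points. A further 10% gives 3.07 × √(0.90 × 0.90) = 2.76 and 87.6%, a gain of 3.6 points.

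**Cost.** Appendix 1 schedules CDR at four post-baseline visits (Weeks 25, 53, 77 and 105), so each covariate with a visit interaction takes four parameters. Two covariates take 8 and three take 12. Assume about 10 parameters in the planned model, which leaves 2 × 243.75 − 10 = 477.5 degrees of freedom. For covariates that explain nothing:
- 3 parameters (three covariates counted at Week 105 only): variance × 477.5 / 474.5 = 1.006, power 79.8%.
- 8 parameters: variance × 477.5 / 469.5 = 1.017, power 79.4%.
- 12 parameters: variance × 477.5 / 465.5 = 1.026, power 79.1%.

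The 8- and 12-parameter rows are upper bounds, because they charge every visit's parameter to the Week 105 contrast. Break-even extra R² is roughly 0.6% to 2.6%.

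**Screening CDR-SB.** This repeats the baseline scale up to 12 weeks earlier. Assume two parallel measurements with reliability 0.80 to 0.95, and a correlation of 0.5 to 0.8 between true baseline and Week 105 score. The extra R² from the second reading is then about 0.01 to 0.12. At the low end it is within the break-even range.

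**The case against.** The best reply is that nothing is broken. The model already holds baseline CDR-SB with its visit interaction, dementia status and APOE ε4, which overlap with any further severity measure. Section 6.1 states "This sample size will have 80% power to detect a true treatment effect of 30% relative reduction" using the SD of the change, and that figure is reached with no help from covariates. A larger SD is handled separately: the blinded SD review in Section 6.1 may raise enrollment to 1126. Entry limits on MMSE, CDR-GS and FCSRT may also narrow the range of severity and weaken severity covariates. All of this stands, and it is why the point is an option and not a defect.

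Deferral of detail to the SAP also counts. Terms may be added there, so the protocol list need not be final. It is still the model as stated.

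Two stronger readings are tempting. A reader might infer from Section 1.1, "The rate of AD progression shows great inter-individual variability with survival dependent on many factors, including age at onset", that the protocol itself says age drives decline on the endpoint. It does not: the sentence ties age at onset to survival, not age at enrollment to two-year CDR-SB change. The baseline measure that the protocol does link to later decline is the FCSRT cueing index (Section 3.3.4, from internal data). That suggests the sponsor may hold data for estimating an R², but it is not evidence for ADAS-Cog-13 or age.

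A reader might also infer that the plan gives power away at no cost. The documents contain no correlation that would show a loss, and added parameters are not free.

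**Conclusion.** The point holds as a cheap improvement. The protocol's primary model leaves out baseline ADAS-Cog-13 and age although both are scheduled for every patient before dosing. Prespecifying them would keep the estimate unbiased and would probably add a little power.

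The size rests on an assumed R². The gain is about 1 to 4 points for an extra 2% to 10% of variance before cost, and 1.8 to 3.6 points for an extra 5% to 10% if the planned terms already explain 10%. The downside is at most about 1 point. The documents do not support calling the trial underpowered, the model wrong, or the gain certain. Screening CDR-SB is the least secure of the three candidates and should be conditional.

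**What to change.** In Section 6.4.1 and the synopsis, and in the SAP, before unblinding:

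- Add baseline ADAS-Cog-13 and age as continuous covariates, each with its interaction with visit.
- Add screening CDR-SB only if prior or blinded data show that it informs Week 105 change beyond Week 1 CDR-SB.
- State a simple rule for missing covariate values, such as mean imputation. Scheduled for every patient does not guarantee recorded for every patient.
- Treat the key secondary models in Section 6.4.2 in the same way.
- Write the model once, in full, so that the list of effects includes the four stratification factors.

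The cost is wording and 8 extra parameters, or 12 if screening CDR-SB is added. No new data or visits are needed. The sponsor could use prior or blinded data to check that the covariates clear the break-even before fixing the list. If the primary model is to stay as it is, the same covariates could go into a prespecified supportive analysis.
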